**Table 10: Key Secondary Analysis – Summary Measures**

Endpoint	Summary Measures
TIS at Week 25	
 
Mean TIS values at Week 25 by treatment sequence
 
Point estimates and 95% CI from MMRM for mean difference (IgPro20 – Placebo) at Week 25
 

Change from Baseline in MMT-8 at Week 25	
 
Mean changes from baseline in MMT-8 at Week 25 by treatment sequence
 
Point estimates and 95% CI from MMRM for mean changes difference (IgPro20 – Placebo) at Week 25
 

Change from Baseline in CDASI total activity score at Week 25	
 
Mean changes from baseline in CDASI total activity score at Week 25 by treatment sequence
 
Point estimates and 95% CI from MMRM for mean changes difference (IgPro20 – Placebo) at Week 25
 

Reduction of oral concomitant corticosteroid dose at Week 25	
 
Point estimate and 95% CI of percentage of subjects who are able to reduce the oral concomitant corticosteroid dose by <math>\geq 25\%</math> at Week 25 by treatment sequence
 
Point estimates and 95% CI for the odds ratio (IgPro20 : placebo) at Week 25
 

#### 10.4.1 Sensitivity Analyses of Key Secondary Endpoints

A tipping point analysis as described in [Ouyang, 2017](#) will be performed as a sensitivity analysis for the continuous key secondary endpoints.

- Tipping point analysis using all available data up to Week 25  
The base case for the tipping point analysis is to include all available data as collected in the MMRM analysis.
  - Replace missing values of scheduled visits which are between two visits with non-missing values (“intermittent missing values”) using the MCMC option in SAS PROC MI by treatment group 50 times to create 50 data sets with only monotone missings.
  - Replace missing values arising after the last scheduled visit (“trailing missing values”) with non-missing values using PROC MI statement using covariates and values from previous visits (1 imputation) regardless of the reason for discontinuation. The result of this imputation will be stored in a separate analysis data set.

- Obtain delta as treatment difference (IgPro20 – placebo) for each post-baseline visit from original MMRM. There will be a separate delta for each visit.
  - Repeat for  $k = 0\%, 100\%, 120\%, 140\%, \dots$ 
    - Subtract  $k \times \text{delta}$  from the imputed trailing values of the IgPro20 arm. Subtraction should stop for an individual value at the worse bound of the variable, ie, at
      - TIS = 0 (lower is worse, values below 0 are not possible),
      - Change from Baseline MMT-8 = – baseline value (lower is worse, changing to below 0 is not possible),
      - Change from Baseline CDASI total activity score = 100 – baseline value (higher is worse, changing to above 100 is not possible)
  - Calculate the MMRM for the 50 imputed data sets and combine the 50 results using PROC MIANALYZE.
  - Stop if one-sided p-value exceeds the significance level according to the Hommel procedure for the respective key secondary endpoint (see Section 4.2.2) or if the worst case imputation for all missing values is reached. The tipping point analysis will only be performed for a variable if the main analysis shows a significant p-value (see Section 4.2.2).
  - Obtain  $k$  at a precision of 1% by iteration.
  - Tipping point analysis excluding data after rescue treatment or withdrawal from IMP  
The tipping point analysis will be repeated under the above-mentioned hypothetical estimand, ie, where data obtained after oral rescue corticosteroid treatment or withdrawal from IMP are excluded from the MMRM analysis.
    - Set all data obtained after oral rescue corticosteroid treatment or withdrawal from IMP for any reason to missing
    - Perform all steps described for the first tipping point analysis above.
-

### 10.4.2 Subgroup Analyses of Key Secondary Endpoints

For the key secondary endpoints subgroup analysis will be done for region (see Section 10.2.2) and for Baseline MMT-8 ( $\leq 142$ ,  $>142$ ).

Subgroup analysis will use the same analytical approach as in the key secondary analysis. For the continuous key secondary endpoints, one MMRM will be performed for each level of subgroup. The test results will be summarized for each level of subgroup, including at least the following: the number of subjects by treatment, the Least Square mean (LS-mean) by treatment, 95% CI for LS-mean by treatment; difference of LS-means with 95% CI and p-value.

## 10.5 Analysis of Secondary Efficacy Endpoint

All secondary efficacy analyses will be performed for the following periods and analysis sets:

- Week 1-25 by treatment sequence (mITT)
- Week 25-53 by treatment sequence (mITT-Ex)

Raw data and changes from the reference visit will be summarized at all visits as appropriate (Table 11). Comparison between treatment sequences will be performed using statistical models as described below. No imputation is planned for missing data in secondary endpoints. P-values from the statistical models are descriptive.

### Continuous variables

- Absolute values and changes from reference visit will be summarized in terms of the number of observations, mean, standard deviation, median, Q1, Q3, minimum, and maximum. A virtual timepoint will be added that describes the last individual visit for each subject per period.
- A MMRM model similar as described in Section 10.4 will be applied. This will be done for each period separately, taking only the visits of the respective period into account. An additional covariate will be the value of the variable at the reference visit of the respective period. The MMRM will analyze the changes from the reference visit.

**TIS**

- Absolute values will be summarized in terms of the number of observations, mean, standard deviation, median, Q1, Q3, minimum, and maximum.
- A MMRM model similar as described in Section 10.4 will be applied. This will be done for each period separately, taking only the visits of the respective period into account. An additional covariate will be the value of TIS at Week 25 for the analysis of period Week 25-53. The MMRM will analyze the absolute values.

**Time to event variables**

- The time to event is calculated by period between the date of event minus the date of the respective reference visit. If the event did not occur in the respective period, the subject is considered censored for the period. The time of censoring for the different endpoints is defined in the table below:

Endpoints	
 
• Time to first achieving TIS <math>\geq</math> 20/40/60 points
 
• Time to meeting DOW for the first time the time
 
	
 
• Time to first intake of oral rescue corticosteroid treatment
 

Time of censoring	
 
• For subjects receiving rescue medication in the period: Date of last assessment of the CSMs (in eCOA) in the respective period before or at the date of starting rescue medication
 
• For subjects not receiving rescue medication in the period: Date of last assessment of the CSMs (in eCOA) in the respective period
 
	
 
• End date of the respective period or
 
• Last day of last week with IMP intake in case of IMP discontinuation in the period
 

	Note: the assessment following IMP discontinuation may be included, the acceptable time window will be defined in the BDRM (see Section 8.2.3).	
--	---	--

In addition to the analyses for Study Period 1, an overall analysis for the combined Study Period 1 and 2 will be performed.

- The time to event will be summarized in terms of the number of observations, number of censored observations, median, Q1, Q3, and the life table output showing the Kaplan-Meier estimates.
- A Cox regression model will be applied for Study Period 1. The model includes effects for treatment, region (Japan vs. non-Japan), and Baseline MMT-8 ( $\leq 142$  points vs.  $>142$  points). The Cox regression will not be done for the whole study duration, as no proportional hazard can be expected.
- An additional exploratory analysis will be added for time to first sustained improvement for each of the categories minimal improvement ( $TIS \geq 20$ ), moderate improvement ( $TIS \geq 40$ ), major improvement ( $TIS \geq 60$ ). Sustained improvement is defined as follows:
  - Improvement met and no oral rescue medication during study period 1 and improvement at Week 25.  
For the calculation of “Time to first sustained improvement” the date of the first time the respective improvement category is met will be used.
  - Subject receiving oral rescue medication or subjects not showing improvement at Week 25 will be considered as not improved and will be censored at the date of last assessment of the CSMs (in eCOA) in study period 1.
  - Subjects discontinued early (without receiving oral rescue medication) will be considered as not improved and will be censored at the date of last assessment of the CSMs (in eCOA) in study period 1.

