At Baseline (Week 1, before infusion of IMP), the site physicians must confirm that no clinically relevant improvement has occurred since the Screening Visit. Clinically relevant improvement is defined as  $\geq 2$  cm improvement on a 10-cm Physician Global Disease Activity Assessment VAS. A sufficient number of subjects will be screened in order to randomize approximately 126 subjects into the study. Subjects will be randomized at a 1:1 ratio to receive either **Sequence A** or **Sequence B** during Study Period 1 and Study Period 2.

During the first 24 weeks of IMP treatment, subjects will receive either IgPro20 0.5 g/kg SC or placebo (Study Period 1); during the subsequent 28 weeks all subjects will receive IgPro20 at a dose of 0.5 g/kg (Study Period 2); and additionally, subjects will be treated with open-label IgPro20 0.5 g/kg SC on a weekly basis until the end of the study (Study Period 3).

If clinically relevant improvement is achieved at Week 17, the subject's concomitant oral corticosteroid dose ( $\leq 20$  mg/day prednisolone equivalent at Baseline) must be tapered downward according to the guidance provided ([Section 5.3.2](#)) and physiotherapy regimen may be modified. Prior to Week 17, the dose of corticosteroids should remain stable unless intolerance or side effects require dose reduction.

In the event of clinical worsening at or after Week 9, site physicians may provide rescue corticosteroid treatment to subjects. Clinical worsening in this study is defined by meeting the criteria for DOW. If an unscheduled visit is used for DOW assessment, the 2 assessments

[figure not shown]
must be done at study visits at least 2 weeks apart. The oral rescue corticosteroid (prednisolone equivalent) treatment should be provided as per the Treating Physician's standard of care (see [Section 5.3.1](#)). Any oral corticosteroid rescue treatment given during the first 24 weeks of randomized IMP treatment should be tapered by Week 25 as much as clinically possible to the corticosteroid dose at Baseline. Subjects who have received rescue corticosteroid treatment before Week 25 will be considered non-responders for the primary endpoint (see [Section 2.1.2](#)) and will continue study participation and IMP treatment. All subjects continuing in the study after Week 25 will receive IgPro20 treatment until Week 53.

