## 5.3 Other Interventions

### 5.3.1 Oral Rescue Corticosteroid Treatment

In the event of clinical worsening (eg, subject meets DOW criteria) between Week 9 and Week 25, the investigator may decide that the subject requires oral rescue corticosteroid treatment for recovery. Intravenous pulse rescue corticosteroid treatment is not permitted.

In this case, the following guidance applies:

- 1 Oral rescue corticosteroid treatment should be given only if DOW criteria are met.
- 2 The earliest that oral rescue corticosteroid treatment can be given is Week 9, to allow for IMP steady state to be achieved. The DOW consists of meeting 1 of the following 3 criteria on 2 consecutive study visits at least 2 weeks apart, up to Week 25:

- a) Physician Global Disease Activity Assessment VAS worsening  $\geq 2$  cm\* and MMT-8 worsening  $\geq$  absolute 10%, - OR -
- b) Extramuscular Global Assessment VAS worsening  $\geq 2$  cm, - OR -
- c) Any 3 of 6 CSMs (see [Section 3.3.1](#)) worsening by  $\geq$  absolute 20%
  - \* If baseline Physician Global VAS is 8 to 10, then any worsening on Physician Global VAS is acceptable as long as MMT-8 criterion is met.

3 The rescue oral corticosteroid (prednisolone equivalent) treatment should be provided as per the Treating Physician's (see [Table 7](#)) standard of care but should not exceed 1 mg/kg/day for up to 5 days.

4 It is recommended that after oral rescue corticosteroid treatment, the oral corticosteroid dose be returned to Baseline dose by Week 25, if clinically possible.

Clinical worsening according to DOW is finished at the first subsequent study visit where none of the criteria are met. A potential next DOW and possible rescue oral corticosteroid treatment can start only after the end of the preceding DOW.

Oral rescue corticosteroid treatment is not permitted in Study Period 2. During Study Period 3, the use of additional oral corticosteroid treatment is permitted. Prior to increasing corticosteroids, investigators should verify that subjects are still benefiting from treatment with IgPro20.

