### **8.2.3 Study Week**

The start of a study week is the day of the first infusion of IMP in that week as recorded in the eCRF. For efficacy, the assessments within 7 days following the IMP discontinuation will be included in the analysis if no rescue medication was administered before the respective assessment.

The end of a study week is the day before the start of the next week. In case of missing exposure weeks as recorded in the eCRF planned weeks will be considered as described below.

- End date of the last non-missing week prior to a missing week is 6 days after its start or one day before the start of the next non-missing week (whatever is first).
- End date of the last missing week is 1 day before the start of the next non-missing week.
- In case of multiple consecutively missing weeks, the total gap time is equally distributed across all missing weeks.

In case there is no gap to include a planned missing week between 2 consecutive non-missing weeks the respective week will be flagged in the listings and the length of the planned week will be 0 (see below).

The end of the last week will be defined as follows:

---

end date of last week = minimum of  
(date of EOP, maximum of (date of 1st infusion in last week + 6 days, date of last administration  
of last week))

For the calculation of average daily dose of oral concomitant corticosteroid treatment, the length  
of a week will be calculated as

$$\text{length of week X (days)} = \text{maximum of (0, end date of week X} - \text{start date of week X} + 1)$$

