**Table 8: Periods and Reference Visits for Study Periods 1 and 2**

Period	Start of period	Reference visit of period	End of period a
For efficacy analysis (TIS):			
Week 1 – Week 25 (Week 1 - EOP1)	Start date and time of the first IMP infusion	Baseline (before infusion of IMP)	Week 25 (before infusion of IMP)
Week 25 – 53/Week 56 b (Week 25 - EOP2)	Start date and time of the first IMP infusion at Week 25	Baseline (before infusion of IMP)	Week 53 (before infusion of IMP)/Week 56
For efficacy analysis (all other endpoints):			
Week 1 – Week 25 (Week 1- EOP1)	Start date and time of the first IMP infusion	Baseline (before infusion of IMP)	Week 25 (before infusion of IMP)
Week 25 – Week 53/Week 56 b (Week 25 - EOP2)	Start date and time of the first IMP infusion at Week 25	Baseline (before infusion of IMP) Week 25 (before infusion of IMP)	Week 53 (before infusion of IMP)/Week 56
For safety analysis:			
Week 1 – Week 25	Start date and time of the first IMP infusion	Baseline (before infusion of IMP)	Week 25 (before infusion of IMP)

Period	Start of period	Reference visit of period	End of period a
(Week 1 - EOP1)			
Week 25 – Week 53/Week 56 b (Week 25 - EOP2)	Start date and time of the first IMP infusion at Week 25	Baseline (before infusion of IMP) Week 25 (before infusion of IMP)	Week 53 (before infusion of IMP)/Week 56
Week 1 – Week 53/Week 56 b (Week 1 - EOP2)	Start date and time of the first IMP infusion	Baseline (before infusion of IMP)	Week 53 (before infusion of IMP)/Week 56

a The end of the period is the listed visit or the last visit before / at withdrawal. For efficacy, the assessments within 7 days following the IMP discontinuation will be included in the analysis if no rescue medication was administered before the respective assessment (see Section 8.2.3). Efficacy assessments for subjects who withdraw from IMP for reasons related to the Ukraine war that are assessed more than 6 weeks after the last IMP administration will be set to missing (see Section 10.2).

b If subjects do not continue treatment after Week 53, an EOP2 Safety Follow-up Telephone Call will be conducted to assess the subject's safety status at Week 56 (or 4 weeks after the final infusion). No efficacy measures will be collected at Week 56.

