### 10.1 Primary Estimand

The primary interest is to quantify the treatment effect of IgPro20

- where the potential confounding effect of oral rescue corticosteroid treatment is excluded
- where the potential confounding of subjects who withdraw from treatment or the study before Week 25 and cannot provide sufficient data to demonstrate a benefit of treatment is excluded, and
- in the absence of premature withdrawal from IMP or the study before Week 25 due to the Ukraine war [[EMA Biostatistics Working Party, 2022](#); [ICH E9 \(R1\), 2020](#)].

The primary estimand in line with the primary interest of the study is described as follows:

- Population: the target patient population defined by eligibility criteria and who received any amount of randomized IMP and have post baseline efficacy results in Study Period 1 (mITT). See Section 6 for details.
- Variable: responder status based on TIS assessments at Weeks 17, 21, and 25
- Intercurrent events:
  - withdrawal from randomized IMP or the study, which is not related to the Ukraine war, or receiving oral rescue corticosteroid treatment before Week 25 is considered treatment failure
  - withdrawal from randomized IMP or the study which is related to the Ukraine war will be addressed using the hypothetical strategy [Meyer et al, 2020; Collins et al, 2020].
- Population-level summary: responder rate by treatment sequence

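### Time to first TIS ≥ 20/40/60: as written, a rescued subject who later reaches the threshold is an event, but one who does not is censored at rescue, so censoring depends on the later outcome

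*SAP*

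**What the plan says.** SAP 10.5 (Time to event variables) works in two steps. It first decides who is censored: "If the event did not occur in the respective period, the subject is considered censored for the period". A table then gives the censoring date. For a subject who receives rescue in the period, time to first TIS ≥ 20/40/60 is censored at "Date of last assessment of the CSMs (in eCOA) in the respective period before or at the date of starting rescue medication". (Time to first DOW shares this row; the point here concerns TIS.) The results feed Kaplan-Meier estimates, a Cox model for Study Period 1, and an overall analysis of Periods 1 and 2 combined.

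Other relevant places:

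- SAP Table 8, footnote a: "The end of the period is the listed visit or the last visit before / at withdrawal". Rescue does not end the period.
- Protocol 3.1: subjects rescued before Week 25 "will continue study participation and IMP treatment", so TIS is still collected after rescue.
- Protocol 5.3.1: "The earliest that oral rescue corticosteroid treatment can be given is Week 9". Up to four scheduled visits (Weeks 13, 17, 21 and 25) can follow a rescue.
- SAP 8.2.3: efficacy assessments "will be included in the analysis if no rescue medication was administered before the respective assessment". This sentence covers only the 7 days after IMP discontinuation.
- SAP 10.4: data after rescue are set to missing, for the MMRM only.
- SAP 10.5, sustained improvement: absence of rescue is part of the event definition, and "Subject receiving oral rescue medication or subjects not showing improvement at Week 25 will be considered as not improved".
- SAP 10.1: for the primary endpoint, "receiving oral rescue corticosteroid treatment before Week 25 is considered treatment failure".

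**The concern.** Rescue corticosteroid is given for worsening. Under the rule as written, two subjects rescued at the same visit are handled differently according to what happens next. The one who later reaches the threshold stays at risk through the rescue and counts as an event. The one who does not is removed at the rescue date. A Kaplan-Meier or Cox risk set must be built from information available at that time, and this one uses the future. It keeps the rescued subjects who improve and drops those who do not, so the improvement curve is pushed up and improvement reached after steroid is credited. No other sentence closes the gap, because the exclusions in SAP 8.2.3, SAP 10.4 and the sustained-improvement definition each cover a different case.

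**Working it through.** **1. Design inputs.** The plan states no figure for this analysis, so its power figure serves only to check the design inputs. From SAP Table 3, the responder rates (response at Week 25 and at Week 17 or 21) are:

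- IgPro20: 0.65×0.9×0.9 + 0.65×0.1×0.2 + 0.35×0.2×0.9 = 0.6025
- Placebo: 0.30×0.9×0.9 + 0.30×0.1×0.1 + 0.70×0.1×0.9 = 0.309

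Exact enumeration of the one-sided Fisher test at 0.025 with 63 per arm gives power 0.904, against 0.905 in SAP Table 14. The inputs reproduce.

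**2. Direction.** Kaplan-Meier is S(t) = Π(1 − d/n) over event times. Compared with following everyone to Week 25, the written rule leaves every event count d unchanged and removes only event-free subjects early. Each n is therefore equal or smaller, and 1 − S is equal or larger at every time. The difference is zero only if nobody is rescued before an event or every rescued subject later improves.

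**3. Worked example (all counts assumed).** There are 63 subjects. Ten are rescued on day 84 without a prior event, and 3 of them reach the threshold on day 140. The other 53 have 5 events at each of days 28, 56, 84, 112, 140 and 168, and 23 have none. Up to day 84 every rule gives S = 48/63. After that:

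| Rule | Calculation of S at day 168 | 1 − S |
|---|---|---|
| As written (7 removed at rescue) | 48/63 × 36/41 × 28/36 × 23/28 = 48/63 × 23/41 | 57.3% |
| All 10 censored at rescue | 48/63 × 33/38 × 28/33 × 23/28 = 48/63 × 23/38 | 53.9% |
| Everyone followed, all events counted | 30/63 | 52.4% (33/63) |
| Rescued kept as not improved | 33/63 | 47.6% (30/63) |

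With 3 rescued (4.8%) and 1 of them improving, the written rule gives 1 − 48/63 × 30/46 = 50.3%. Censoring all three gives 1 − 48/63 × 30/45 = 49.2%, and full follow-up gives 31/63 = 49.2%. The excess is 1.1 points.

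**4. Range.** Simulations of 400,000 subjects per scenario assumed 1.5% to 14% rescued before any event. At day 168 the written rule exceeded full follow-up by 0.2 to 4.1 points, censoring everyone at rescue by 0.1 to 7.3 points, and rescue as not improved by 0.9 to 11.4 points. In 3,000 simulated arms of 63 it was never below full follow-up or censor-at-rescue at day 168. Against censor-at-rescue that ordering is not assured at earlier times, because later improvers remain in the risk set until their event.

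**5. On the scale of one arm.** This simulation used the plan's Week 17 rates (30% and 65%) and new-response rates (10% and 20% per later visit), for TIS ≥ 20 only. Rescue rates and a 20% to 40% chance of reaching TIS ≥ 20 after rescue are assumptions. SE = √(p(1−p)/63), and shifts are measured from rescue as not improved.

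| Arm, rescued | Written rule | Censor all at rescue | Part removed by the fix (difference) |
|---|---|---|---|
| Placebo, 5% | 0.31–0.44 SE | not reported | below 0.44 SE |
| Placebo, 10% | 0.64–0.90 SE | 0.36 SE | 0.28–0.54 SE |
| Placebo, 15% | 0.99–1.39 SE | 0.55 SE | 0.44–0.84 SE |
| IgPro20, 5% | 0.54–0.64 SE | 0.43 SE | 0.11–0.21 SE |

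**6. Treatment comparison.** With 10% placebo and 5% IgPro20 rescue, rescue as not improved gives 75.3 − 41.0 = 34.3 points. The written rule gives 78.2 − 45.0 = 33.2 to 78.8 − 46.6 = 32.2 points. The change is 1.1 to 2.1 points, about 0.13 to 0.25 SE of the difference. The Cox hazard ratio moves from 2.53–2.54 to 2.48–2.41, against IgPro20. With 5% rescue in both arms it rises from about 2.45 to 2.48–2.51.

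**The case against.** The SAP never says outright that a threshold reached after rescue counts. Setting a rescued subject's censoring date at rescue would normally mean that follow-up ends there, and neither the MMRM nor the sustained-improvement analysis credits improvement after rescue. The authors may well have meant to censor every rescued subject at rescue. That is a fair reading of intent, but the order of the rules gives a programmer the other result.

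The endpoint lies outside the gatekeeping family and its p-values are descriptive (SAP 10.5). This stands in full.

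Protocol 3.3.1 does not expect many flares meeting DOW, and DOW needs two consecutive visits. This stands for Study Period 1, with two qualifications. A dose increase above 125% of Baseline after taper also counts as rescue (Protocol 5.3.2, SAP 10.2). In the combined-period analysis, a placebo subject rescued in Period 1 could have the event on IgPro20 in Period 2.

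A reader might infer that rescue has to be a failure here because the primary endpoint treats it so, and that censoring at rescue is itself wrong. The documents do not support this. SAP 10.3 declares a hypothetical interest without rescue for the key secondary endpoints, and censoring at rescue fits that aim, although it assumes that rescued subjects would otherwise have improved like the rest. Sustained improvement is a separately defined exploratory endpoint, so its different handling is not a contradiction.

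**Conclusion.** The defect holds for the rule as written. Censoring of rescued subjects depends on their later outcome, and 1 − Kaplan-Meier is biased upward relative to full follow-up whenever a subject rescued before an event does not later reach the threshold. The direction is certain and the size is not. It rests on assumed rescue and post-rescue improvement rates, and single-arm figures were run only for TIS ≥ 20. At 5% rescue or less the placebo shift is under about half an SE, even measured against rescue as not improved. On that measure IgPro20 at 5% is slightly above half an SE, mostly from the choice between censoring and failure.

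A reader might also infer that improvement is materially overstated or that the treatment comparison is distorted in favour of IgPro20. Neither is shown. The contrast between arms moves little, and when more placebo than IgPro20 subjects are rescued it moves against IgPro20. The primary and key secondary tests are untouched. This is a correction to one rule for a descriptive secondary endpoint.

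**What to change.** In the SAP 10.5 censoring table, for time to first TIS ≥ 20/40/60, state that:

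- only a threshold first reached on or before the start of rescue counts as an event;
- every other rescued subject is censored at the last CSM assessment before or at rescue, whatever happens afterwards;
- the same rule applies to the Kaplan-Meier, Cox and combined Period 1 and 2 analyses.

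A cumulative-incidence display with rescue as a competing event, or with rescued subjects kept event-free to the end of the period, may be added as a supplementary view. It is an estimand choice and not a required replacement. It should not be described as identical to the primary or sustained-improvement rule, since in both of those a subject who improves and is rescued later in Study Period 1 also fails.

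The cost is one wording change and a reprogrammed event and censoring flag. The same table cell needs editing anyway, because its note still leaves the window after IMP discontinuation to the BDRM while SAP 8.2.3 fixes it at 7 days. The downside is that estimated improvement rates become slightly lower.

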## 4.3 Discontinuation of IMP and Subject Study Withdrawal

### 4.3.1 Discontinuation of IMP

If any of the following apply, the subject must discontinue IMP:

- Subject wishes to discontinue IMP
- Subject withdraws consent for study participation
- Investigator advises that the subject's safety or well-being could be compromised by further treatment
- Subject or caregiver is not able to administer the SC infusions at home by Week 4
- Subject has confirmed diagnosis of DVT or PE
- Subject has Grade 3 hemolysis (see [Section 8.1.2.3](#))
- Subject becomes pregnant
- Relevant treatment noncompliance

During participation in Study Period 3, if the investigator determines that the subject is no longer benefiting from IgPro20 and/or is showing signs of clinical deterioration in DM status, the subject must be discontinued from the study.

The investigator should record in the electronic case report form (eCRF) and in the subject's medical records the reason and date of IMP discontinuation.

Subjects who discontinue IMP will be encouraged to remain in the study until Week 25 if discontinuation occurs during Study Period 1, or until Week 53 if discontinuation occurs during Study Period 2, in order to collect study assessments. The Safety Follow-up Telephone Call will not be performed for subjects who discontinue IMP treatment but remain in the study for at least 1 subsequent study visit 4 weeks after IMP discontinuation. See [Schedule of Assessments](#) for details on assessments no longer collected after IMP discontinuation if the subject remains in the study, and Section 4.3.2 for details on handling subject withdrawal from study.

Subjects who discontinue IMP during Study Period 3 will be withdrawn from the study. Withdrawal from IMP Study Period 1 or Study Period 2 renders a subject ineligible for participation in Study Period 3 of this study.

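### In the exploratory time-to-sustained-improvement analysis, early leavers are known non-events but are censored at their last assessment, so Kaplan-Meier overstates the proportion with sustained improvement

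*SAP*

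**What the plan says.** SAP 10.5 (Time to event variables) introduces the analysis: "An additional exploratory analysis will be added for time to first sustained improvement". It is run for each of the three TIS categories (20, 40 and 60 points).

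- **Event:** "Improvement met and no oral rescue medication during study period 1 and improvement at Week 25".
- **Event date:** "the date of the first time the respective improvement category is met will be used".
- **Rescued subjects and Week 25 failures:** "Subject receiving oral rescue medication or subjects not showing improvement at Week 25 will be considered as not improved". They are censored at the last core set measure (CSM) assessment in Study Period 1.
- **Early discontinuers:** "Subjects discontinued early (without receiving oral rescue medication) will be considered as not improved and will be censored at the date of last assessment", again of the CSMs in Study Period 1.
- **Summary for time-to-event variables:** it includes "number of censored observations, median, Q1, Q3, and the life table output showing the Kaplan-Meier estimates".

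Two other rules bear on how long a subject who stops study drug is followed. Protocol 4.3.1 says: "Subjects who discontinue IMP will be encouraged to remain in the study until Week 25". SAP 8.2.3 says: "For efficacy, the assessments within 7 days following the IMP discontinuation will be included in the analysis", provided no rescue was given before the assessment.

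SAP 10.1 counts withdrawal before Week 25 as treatment failure in the primary estimand, except when it is related to the Ukraine war. Those withdrawals are handled by a hypothetical strategy.

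**The concern.** Kaplan-Meier censoring means that the outcome after the censoring time is unknown and that the subject would have had the event at the same rate as those still under observation. Here the outcome is known. The definition requires improvement at Week 25, so a subject who is gone by Week 25 is a non-event, and the SAP says as much. Removing that subject from the risk set before Week 25 shrinks the denominator at later visits without removing any events, and the estimated cumulative proportion rises.

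At stake is the descriptive reading of these curves: the Week 25 proportion with sustained improvement, the quartiles read from the curve, and the apparent gap between arms.

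**Working it through.** **Inputs.** SAP Table 3 gives Week 17 response of 0.65 (Sequence A) and 0.30 (Sequence B). The probability of response after a response at the previous visit is 0.9 in both arms. After a non-response it is 0.2 (A) and 0.1 (B). There are 63 subjects per arm. No dropout rate is given, because SAP 14.1.2 folds withdrawal into non-response. Dropout of 5%, 10% and 20% is therefore assumed.

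**Step 1: reproduce the plan's figures.** The primary responder needs Week 25 and at least one of Weeks 17 and 21.
- A: 0.65×0.9×0.9 + 0.65×0.1×0.2 + 0.35×0.2×0.9 = 0.6025
- B: 0.30×0.9×0.9 + 0.30×0.1×0.1 + 0.70×0.1×0.9 = 0.309

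Exact one-sided Fisher power at 63 per arm and level 0.025 is 0.904. SAP Table 14 gives 0.905, so the inputs are read correctly.

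**Step 2: rates for the sustained endpoint.** Sustained improvement needs Week 25 but not Week 17 or 21, because the first qualifying visit may be Week 25 itself. Add the path with no response at Weeks 17 and 21 and response at Week 25.
- A: 0.6025 + 0.35×0.8×0.2 = 0.6025 + 0.056 = 0.6585
- B: 0.309 + 0.70×0.9×0.1 = 0.309 + 0.063 = 0.372

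These apply to TIS ≥ 20. The plan gives no rates for 40 or 60.

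**Step 3: Kaplan-Meier under the SAP rule.** Let p be the true proportion and d the dropout proportion. Events are spread evenly over six visits (Weeks 5, 9, 13, 17, 21, 25), so e = p/6. Dropouts are censored evenly over the first five, so c = d/5. At visit k the risk set is n_k = 1 − (k−1)(e + c), and 1 − KM = 1 − Π(1 − e/n_k).

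At 10% dropout, c = 0.02:
- A: e = 0.10975. Risk sets are 1, 0.870, 0.741, 0.611, 0.481, 0.351. Factors are 0.890, 0.874, 0.852, 0.820, 0.772, 0.688, with product 0.288. 1 − KM = 0.712.
- B: e = 0.062. Risk sets are 1, 0.918, 0.836, 0.754, 0.672, 0.590. The product of the factors is 0.604. 1 − KM = 0.396.

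The same recursion with c = 0.01 and 0.04 gives the other rows:

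| Dropout per arm | A (true 0.659) | B (true 0.372) | Difference (true 0.287) |
|---|---|---|---|
| 5% | 0.683 | 0.384 | 0.300 |
| 10% | 0.712 | 0.396 | 0.315 |
| 20% | 0.786 | 0.427 | 0.359 |

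**Step 4: unequal dropout.** With 5% in A and 20% in B the difference is 0.683 − 0.427 = 0.257 from unrounded values, below the true 0.287. With 20% in A and 5% in B it is 0.786 − 0.384 = 0.402, above it.

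**Step 5: sensitivity to timing.** The excess is smaller when dropout is late or events are early. At the primary-responder rates (0.6025 and 0.309), early, even and late timings of events and dropout gave an excess at 10% dropout of about 1 to 6.6 points in A and 0.3 to 3.3 points in B. Kaplan-Meier exceeded the true proportion in every scenario tried.

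**Step 6: the alternative.** If non-events stay in the risk set to Week 25, set c = 0. The product then telescopes to 1 − p, so 1 − KM equals 0.6585 and 0.372 at any dropout rate.

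**The case against.** The strongest reply is that little depends on this. The analysis is exploratory, its p-values are descriptive, and the primary analysis already counts non-war withdrawals as failures. A supplementary analysis at TIS ≥ 40 follows the same approach. All of that stands.

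A second reply is that the rule refers to the last CSM assessment in Study Period 1, not to the day study drug stops. Subjects who stop study drug are encouraged to stay to Week 25. Anyone assessed to Week 25 is censored there, and no bias arises. That also stands on the literal text, although the 7-day rule in SAP 8.2.3 may put the last usable assessment close to the stop of study drug.

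Some stronger readings are tempting, but the documents do not support them:
- **That Kaplan-Meier treats leavers as if they would all improve.** It gives them the rate of subjects still at risk.
- **That the SAP handles different kinds of failure under different rules.** Both bullets state the same rule. Only the length of follow-up differs, and rescued subjects who leave early share the problem.
- **That the bias is always larger in the arm with more discontinuations.** It also rises with the event rate. At equal 10% dropout the excess is 0.712 − 0.659 = 0.053 in A and 0.396 − 0.372 = 0.024 in B.
- **That censoring is why these curves would disagree with the primary analysis.** The definitions differ (Step 2), so the two would differ with no dropout at all.

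**Conclusion.** The point holds for the exploratory sustained-improvement curves. Classing early leavers as not improved conflicts with censoring them before Week 25, and the cumulative proportion is biased upward. For TIS ≥ 20 with even timing, the overstatement is about 2 points (A) and 1 point (B) at 5% dropout, 5 and 2 points at 10%, and 13 and 5 points at 20%. Those figures rest on assumed dropout rates and timing and on the Table 3 response rates. The direction in each arm does not depend on the particular values, provided some subjects leave before the last events occur. The direction for the arm difference is not determined. The effect on a Cox hazard ratio was not calculated.

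A reader might infer that the trial's efficacy conclusion is in doubt. It is not: the primary and key secondary tests do not use this analysis.

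**What to change.** Change the censoring wording in SAP 10.5 so that every subject classed as not improved (early discontinuers for reasons unrelated to the war, rescued subjects, and Week 25 non-improvers) is censored at the nominal end of Study Period 1, Week 25. Equivalently, report cumulative incidence with discontinuation and rescue as competing events.

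State an exception for war-related withdrawals: keep them censored at their last assessment. Counting them as failures would conflict with the hypothetical strategy in SAP 10.1, and the sustained-improvement rule does not currently mention them.

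It would also help to report the plain proportion with sustained improvement beside the curve.

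The cost is one wording change in the SAP and somewhat lower reported curves. No new data are needed.
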